### 6.6.2.1 Repriming for Magrolimab

Given the large CD47 antigen sink on normal cells, subjects who have a dose delay of magrolimab equivalent to 28 days or more are required to be reprimed with magrolimab to resaturate the CD47 antigen sink. Within 24 hours prior to each of the repriming doses of magrolimab, all subjects must have a documented Hgb  $\geq 9$  g/dL. Subjects who do not meet these criteria must be transfused and

have their Hgb rechecked to meet the minimum Hgb threshold prior to each of the first 2 doses of magrolimab. During the first 2 doses of repriming, blood testing of Hgb will be required 3 to 6 hours after a magrolimab dose and the results must be reviewed prior to discharging the subject from clinic. The subject should be transfused as clinically appropriate.

Repriming differs depending on where the participant is in their treatment period as follows:

- 1) For subjects who have not reached Day 57 of magrolimab, up to 14 days between doses is permitted.
- 2) For subjects who have received Day 57 (or beyond) dose of magrolimab, up to 28 days between doses is permitted.

After Day 22 of repriming, subjects should return to their original maintenance dose schedule.

Please notify the Medical Monitor of any planned dose delays.

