d If magrolimab is not administered for 28 days or more and then restarted, the resulting doses, called repriming doses, follow the same schedule and dose level as the first 22 days of the priming doses, then maintenance dosing can start 7 days later. For subjects who have not received at least one 30 mg/kg dose of magrolimab, a dose delay of only 14 days is allowed until repriming is required. Within 24 hours prior to each of the repriming doses of magrolimab, all subjects must have a documented Hgb  $\geq 9$  g/dL. Subjects who do not meet these criteria must be transfused and have their Hgb rechecked to meet the minimum Hgb threshold prior to each of the first 2 doses of magrolimab. During the first 2 doses of repriming, blood testing of Hgb will be required 3 to 6 hours after a magrolimab dose and the results must be reviewed prior to discharging the subject from clinic.

A CBC is needed before each dose during the repriming cycle. Within 24 hours prior to each of the first 2 repriming doses of magrolimab, all subjects must have a documented Hgb  $\geq 9$  g/dL. Subjects who do not meet these criteria must be transfused and have their Hgb rechecked to meet the minimum Hgb threshold prior to each of the first 2 repriming doses of magrolimab. Magrolimab should be infused over 3 hours ( $\pm 30$  minutes) following the repriming dose schedule (1 mg/kg on Days 1 and 4; 15 mg/kg on Day 8; and 30 mg/kg on Days 11, 15, 22.). Days are adjusted depending on when repriming occurs. During the first 2 doses of repriming, blood testing of Hgb will be required 3 to 6 hours after a magrolimab dose and the results must be reviewed prior to discharging the subject from the clinic. The subject should be transfused as clinically appropriate. Vital signs, weight, reporting of concomitant medications/transfusions/AEs, premedications, chemistries, and urinalysis follow the same schedule as given for priming in [Table 2](#).

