When both study drugs are given on the same visit day, magrolimab will be administered at least 1 hour after oral decitabine/cedazuridine administration.

Magrolimab doses will be given twice weekly during priming and escalation (2 weeks), with a window of  $\pm 3$  days for each dose; however, magrolimab doses are not to be given on consecutive days. If additional delay is needed to ensure a white blood cell (WBC) of  $\leq 20 \times 10^3/\mu\text{L}$ , please contact the sponsor's medical monitor.

During the first 28 days of treatment (Days 1, 4, 8, 11, and 22), WBC count must be  $\leq 20 \times 10^3/\mu\text{L}$  prior to each magrolimab dose. Subjects with WBC  $> 20 \times 10^3/\mu\text{L}$  can be treated with hydroxyurea (up to 4 g/day) during the first 56 days to reduce the WBC to  $\leq 20 \times 10^3/\mu\text{L}$ .

Within 24 hours prior to each of the first 2 priming or repriming doses of magrolimab, all subjects must have a documented hemoglobin (Hgb)  $\geq 9 \text{ g/dL}$ . Subjects who do not meet these criteria must be transfused and have their Hgb rechecked to meet the minimum Hgb threshold prior to each of the first 2 doses of magrolimab. During the first 2 doses of priming and repriming, blood testing of Hgb will be required 3 to 6 hours after a magrolimab dose and the results must be reviewed prior to discharging the subject from the clinic. The subject should be transfused as clinically appropriate. Investigators should consider additional Hgb monitoring during the first week of treatment in subjects with symptoms of anemia or increased risk for complications of anemia.

All subjects should be monitored hourly during infusion and for 1 hour after infusion for doses during the first 28 days and the repriming doses. Subjects should be monitored (including measurement of vital signs, as clinically appropriate) for signs and symptoms of infusion-related reactions, which have been observed in previous magrolimab studies.

Postinfusion monitoring is not required for doses after Day 22 of priming or repriming. Subjects who experience any treatment-related AEs prior to this point should be further monitored as

clinically appropriate. Management of infusion-related reactions is further described in Section 8.5.7.2.

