## **8.5.7 Specific Safety Management Guidelines**

### **8.5.7.1 Anemia, Blood Cross-matching, and Packed Red Blood Cell Transfusion Procedures**

Magrolimab binds to RBCs and leads to erythrophagocytosis. In clinical studies, anemia is the most common treatment-related AE and is typically manifested as a decline in Hgb observed in the first 1 to 2 weeks of treatment. Subjects with low baseline Hgb level, especially those with cardiac history, should be monitored closely after initial administrations of magrolimab as preexisting anemia could be exacerbated. In general, a Hgb level of at least 9.5 g/dL or higher for subjects with cardiac comorbidities prior to the first magrolimab dose is recommended. Hgb  $\geq 9$  is required prior to the first two doses in priming and repriming of magrolimab. Red blood cell transfusions are permitted prior to study treatment to ensure adequate Hgb level. This, coupled with anemia from other causes in participants with cancers, means that care has to be taken with RBC cross-matching and packed RBC transfusions. There is a possibility that treatment with magrolimab may obscure assessment of RBC phenotyping, although this has not been observed in the subjects treated to date.

Prior to initiation of magrolimab, extended RBC phenotyping or genotyping for minor antigens, type and screen (ABO/Rh), and DAT will be performed for each subject as described in Section 5.3.3. This, together with using the prior phenotype, will facilitate allocation of properly matched blood, should a blood transfusion be warranted.

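### For magrolimab repriming, the protocol contradicts itself on whether the pre-dose hemoglobin threshold applies to all six doses or only the first two

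*Combined protocol and SAP*

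**What the plan says.** **Hgb before repriming, applied to every dose.** Section 6.6.2.1 sets the Hgb ≥9 g/dL requirement "Within 24 hours prior to each of the repriming doses of magrolimab". The first paragraph of Table 4 note d (Section 1.3) does the same: "Within 24 hours prior to each of the repriming doses of magrolimab, all subjects must have a documented Hgb" at or above that level. In both places the next sentence says that subjects below the threshold must be transfused and "have their Hgb rechecked to meet the minimum Hgb threshold prior to each of the first 2 doses of magrolimab".

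**Hgb before repriming, applied to two doses.** The second paragraph of note d reads "Within 24 hours prior to each of the first 2 repriming doses of magrolimab, all subjects must have a documented Hgb" at the same level. Section 4.5 applies the rule "Within 24 hours prior to each of the first 2 priming or repriming doses of magrolimab". Section 8.5.7.1 says that the threshold "is required prior to the first two doses in priming and repriming of magrolimab".

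**Blood counts.** The second paragraph of note d also calls for a complete blood count (CBC) before each dose of the repriming cycle. Table 2 schedules a CBC at every priming dose day, Day 15 included.

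**White cell limit.** Section 4.5 sets a limit of 20 × 10³/µL, introduced by "During the first 28 days of treatment (Days 1, 4, 8, 11, and 22" and stated as applying before each magrolimab dose. Table 6 also gives a dose on Day 15. Inclusion criterion 10 applies the same limit before the first dose and for the whole study.

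**The concern.** The Hgb requirement decides whether a dose may be given. Take a subject whose Hgb is below 9 g/dL before the Day 8 repriming dose. Under Section 6.6.2.1 that subject does not meet a mandatory condition for dosing. Under Sections 4.5 and 8.5.7.1 no threshold is set for that dose. The same infusion is then a protocol deviation by one section and compliant by another. Section 4.4 plans about 58 sites, and Section 8.0 rules out waivers, so sites and monitors need a single answer.

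The matter bears on patient safety. Section 8.5.7.1 describes anemia as the leading treatment-related adverse event with magrolimab, typically appearing in the first week or two. The doses in dispute include the step to 15 mg/kg on Day 8 and the step to 30 mg/kg on Day 11.

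**Working it through.** No sample size, power or error rate enters this point, and the plan states no figure to reproduce. The check compares the dosing days with the days that each statement covers.

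**Step 1: repriming doses.** Table 4 note d gives 1 mg/kg on Days 1 and 4, 15 mg/kg on Day 8, and 30 mg/kg on Days 11, 15 and 22. That is 2 + 1 + 3 = 6 doses.

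**Step 2: what each statement covers.**

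| Place | Threshold applies to | Transfuse and recheck applies to |
|---|---|---|
| Section 6.6.2.1 | all 6 repriming doses | first 2 |
| Table 4 note d, first paragraph | all 6 repriming doses | first 2 |
| Table 4 note d, second paragraph | first 2 repriming doses | first 2 |
| Section 4.5 | first 2 priming or repriming doses | first 2 |
| Section 8.5.7.1 | first 2 priming and repriming doses | not stated |

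**Step 3: doses in conflict.** Both rules cover Days 1 and 4. The remaining 6 − 2 = 4 doses (Days 8, 11, 15 and 22) carry the threshold under two statements and not under the other three.

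**Step 4: the wider rule is incomplete.** In the first two rows the threshold reaches 6 doses but the action for a low value reaches 2. For the other 4 doses, a site following the wider rule has a condition to meet and no stated step when it is not met.

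**Step 5: initial priming.** Table 4 note a, Section 4.5 and Section 8.5.7.1 all name the first 2 priming doses. There is no conflict there.

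**Step 6: white cell day list.** Table 6 doses on Days 1, 4, 8, 11, 15 and 22 within the first 28 days, which is 6 doses. Section 4.5 lists 5 days. The missing one is 6 − 5 = 1 day, Day 15.

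**The case against.** The first-two wording appears in three of the five places. The post-dose Hgb test is limited to the first 2 doses throughout, and even the every-dose paragraphs revert to the first 2 in their next sentence. A reader could fairly conclude that the every-dose wording is a drafting slip. That may be so, but Section 6.6.2.1 is the section dedicated to repriming, and note d states both rules within one footnote. Counting occurrences does not settle which rule governs.

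A reader might infer that repriming doses 3 to 6 could be given with no blood count at all. The documents do not support that, because note d requires a CBC before each repriming dose. Only the threshold and its 24-hour documentation are in doubt. The timing is not quite covered by the CBC rule: Table 2 note d accepts a count from the day before for doses after the first 2, and such a count could fall outside 24 hours.

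A reader might also infer that the Day 15 dose is exempt from the white cell limit. It is not. The sentence in Section 4.5 covers each dose in the first 28 days, criterion 10 applies the limit throughout, and nothing exempts Day 15. The list is simply one day short.

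The reach is also limited. Repriming follows only a gap of 28 days or more, or a shorter 14-day limit earlier in treatment, and Section 6.6.2 says that magrolimab delays should generally be avoided. This objection stands in full.

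**Conclusion.** The contradiction on the Hgb threshold is real, sits in the current text and is confined to repriming. It affects 4 of the 6 doses in each completed repriming course. If r such courses are given, the number of doses under conflicting instructions is 4 × r. The documents give no expected value of r, so the number of subjects or doses affected cannot be stated.

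Adverse events are part of the primary endpoint, so a reader might infer that the primary safety or efficacy results would be distorted. Nothing in the documents shows this. Adverse events are summarized descriptively in a single arm (Section 9.3.1), and sample size, power and error rates are untouched. The case for correction rests on subject safety and on having one rule that sites can follow. The white cell list is an editorial matter only.

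The conclusion assumes that the statements are meant to describe one rule. No passage says that one section overrides another. I take no view on which rule is right.

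**What to change.** Reconcile Section 4.5, Section 6.6.2.1, Section 8.5.7.1 and both paragraphs of Table 4 note d so that the Hgb threshold, its 24-hour documentation and the transfuse-and-recheck step name the same repriming doses in every place. The sponsor decides which rule applies. If the threshold is meant to extend beyond the first 2 doses, the text also needs to state what happens when it is not met, and Table 2 note d should agree on the timing of the count.

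As an editorial correction, make the day list for the white cell limit in Section 4.5, inclusion criterion 10 and the dosing days in Table 6 agree.

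The change is wording only. CBCs are already scheduled at all of these doses, so no visit or test is added; at most the permitted timing of an existing count would change.

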#### 4.5 Dosing Administration

The treatment administration schedule for oral decitabine/cedazuridine and magrolimab is presented in [Table 5](#) and [Table 6](#). The detailed PK assessment schedule is presented in [Table 13](#) and [Table 14](#).

The following magrolimab dosing regimen is proposed for this study:

- The dose of magrolimab is increased over time in a series called priming doses. Priming doses of magrolimab: 1 mg/kg on Days 1 and 4; 15 mg/kg on Day 8; 30 mg/kg on Days 11, 15, 22, 29, 36, 43, and 50.
- Maintenance doses of magrolimab: 30 mg/kg on Day 57 and every 14 days thereafter.
- If magrolimab is not administered for 28 days or more and then restarted, the resulting doses, called repriming doses, follow the same schedule and dose level as the first 22 days of the priming doses, then maintenance dosing can start 7 days later. For subjects who have not received at least one 30 mg/kg dose of magrolimab (ie, for subjects who have either not received their first dose of 30 mg/kg or subjects who have received doses <30 mg/kg), a dose delay of only 14 days is allowed until repriming is required.

The duration of each magrolimab infusion including flush will be 3 hours ( $\pm 30$  minutes) for the first 3 doses of priming and repriming. Recommended premedications are listed in [Section 6.5](#). After the third dose of treatment, the magrolimab infusion including flush will be 2 hours ( $\pm 30$  minutes). The reduced infusion time to 2 hours is based on prior data demonstrating the majority CD47 receptor occupancy (RO) on peripheral blood cells, thus mitigating anticipated RBC toxicities from magrolimab.

Oral decitabine/cedazuridine study treatment is to be administered according to the following schedule:

- Days 1-5: oral decitabine/cedazuridine by mouth daily on an empty stomach (morning before breakfast) with no food for 2 hours before and at least 2 hours after administration. When taking oral decitabine/cedazuridine, subjects may have clear liquids such as water, black coffee, or tea. The dosing regimen may be modified during assessment of DLTs in the DLT cohort ([Section 4.1.1](#)).

**Table 5:** Treatment Administration Schedule for Oral Decitabine/Cedazuridine

Day →	1	2	3	4	5	6-28
All Cycles	×	×	×	×	×	—

DLT=dose-limiting toxicity; FDC=fixed-dose combination; "×"=dosing day; "—"=non-dosing day

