**Table 6: Treatment Administration Schedule for Magrolimab**

Day →	1	2-3	4	5-7	8	9-10	11	12-14	15	16-21	22	23-28
Dose (mg/kg)	1	—	1	—	15	—	30	—	30	—	30	—
<hr/>												
Day →	29	30-35	36	37-42	43	44-49	50	51-56	57	58-70	71	72-84
Dose (mg/kg)	30	—	30	—	30	—	30	—	30	—	30	—

Note: The dose of magrolimab is increased from 1 mg/kg to 30 mg/kg during priming on Days 1-56. Maintenance doses continue after priming at 30 mg/kg, starting at Day 57 and every 14 days thereafter. If magrolimab is not administered for 28 days or more and then restarted, the resulting doses, called repriming doses, follow the same schedule and dose level as the first 22 days of the priming doses, then maintenance dosing can start 7 days later. For subjects who have not received at least one 30 mg/kg dose of magrolimab, a dose delay of only 14 days is allowed until repriming is required.

Alternative options for oral decitabine/cedazuridine administration on Days 1-5 are detailed in [Table 7](#).

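### The magrolimab repriming rules contradict each other on when repriming is required and on how long repriming infusions last

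*Combined protocol and SAP*

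**What the plan says.** **Trigger.** Section 4.5 gives the general rule: "If magrolimab is not administered for 28 days or more and then restarted, the resulting doses, called repriming doses" repeat the schedule of the first 22 priming days. It then makes an exception for anyone still without a 30 mg/kg dose, worded as "a dose delay of only 14 days is allowed until repriming is required". The synopsis (Section 1.1), Table 2 note b, Table 4 note d and the note to Table 6 carry the same rule and exception. Sections 1.1 and 4.5 add a bracket that extends the exception to subjects who have received doses below 30 mg/kg; the three tables do not.

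Section 6.6.2.1 opens by requiring repriming for any subject whose dose delay amounts to 28 days or more. Two items follow: "For subjects who have not reached Day 57 of magrolimab, up to 14 days between doses is permitted" and "For subjects who have received Day 57 (or beyond) dose of magrolimab, up to 28 days between doses is permitted".

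**Infusion time.** Table 2 note b sets 3 hours for the first three doses of treatment and 2 hours afterwards. Section 4.5 sets 3 hours for the first three doses of priming and of repriming. The text below Table 4 says "Magrolimab should be infused over 3 hours" and ties this to the repriming schedule, listing all six doses.

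**After repriming.** The note to Table 6 says "then maintenance dosing can start 7 days later", as do Section 4.5 and Tables 2 and 4. Section 6.6.2.1 says "After Day 22 of repriming, subjects should return to their original maintenance dose schedule".

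**The concern.** A site that meets a missed-dose gap during priming has to decide whether the next infusion is a first repriming dose or the scheduled dose. The protocol answers in six places, and the answers differ.

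Section 6.6.2.1 gives repriming a purpose, which is to refill the CD47 antigen sink on normal cells, and requires hemoglobin checks around it. The choice therefore changes both the next dose and the monitoring that goes with it. Delays are foreseen: Section 6.6.2 puts dose delay before dose reduction for severe magrolimab-related events. About 58 sites must apply the rule (Section 4.4), and Section 8.0 allows no waivers, so a site that follows one text departs from another.

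Adverse events are part of the primary endpoint (Section 3.0). Uneven handling of the same gap could add variation to those data that reflects the wording of the protocol and not the combination under study.

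**Working it through.** No sample-size, power or error-rate formula applies. The check is to apply each rule literally to the same last dose and the same gap.

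**Inputs (Section 4.5, Table 6).** Priming doses fall on Days 1, 4, 8, 11, 15, 22, 29, 36, 43 and 50. Those from Day 11 on are 30 mg/kg. Maintenance starts on Day 57 and runs every 14 days. Repriming has six doses, on Days 1, 4, 8, 11, 15 and 22.

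**Rules.**
- A (Sections 1.1 and 4.5; Tables 2, 4 and 6): reprime at 28 days or more, or beyond 14 days if no 30 mg/kg dose has been given.
- B (Section 6.6.2.1, items 1 and 2): reprime beyond 14 days before the Day 57 dose, or beyond 28 days from it.
- C (Section 6.6.2.1, opening sentence): reprime at 28 days or more for everyone.

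**Assumptions.** A gap is the number of days between doses. Exceeding the permitted gap means repriming. Position in the schedule is judged by doses received. If reaching Day 57 were judged by the calendar, some late-priming gaps would leave item 1: a last dose on Day 43 plus 15 days is Day 58, and that subject, without the Day 57 dose, would fit neither item.

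| Last dose | A against B | C against B |
|---|---|---|
| Days 1, 4, 8 | agree | disagree at 15–27 days |
| Days 11 to 50 (7 of 10 priming doses) | disagree at 15–27 days | disagree at 15–27 days |
| Day 57 onward | disagree at exactly 28 days | disagree at exactly 28 days |

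Example: last dose on Day 22, gap of 20 days. Under A, 20 < 28 and a 30 mg/kg dose has been given, so there is no repriming and the next dose is 30 mg/kg. Under B, 20 > 14, so repriming starts at 1 mg/kg. The next dose differs by a factor of 30/1 = 30.

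**The bracket in Sections 1.1 and 4.5.** Read literally, it may also cover subjects reduced to 20 or 15 mg/kg under Section 6.6.2. For them Section 4.5 would apply 14 days even after Day 57, where item 2 and Tables 2, 4 and 6 do not.

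**Delay against interval.** The texts move between a dose delay and days between doses as if these were the same. Counted from the due date, a 14-day delay is an interval of 7 + 14 = 21 days in weekly dosing and 14 + 14 = 28 days in maintenance. A 28-day delay is 7 + 28 = 35 and 14 + 28 = 42 days.

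**Infusion time.** For a subject who has already had three doses, the number of 3-hour infusions among the six repriming doses is:
- Table 2 note b, read literally: 0
- Section 4.5: 3
- text below Table 4: 6

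**After repriming.** Starting 7 days later gives repriming Day 22 + 7 = 29. Running the 14-day interval from the last repriming dose gives 22 + 14 = 36. Returning to the subject's own calendar gives a third date, which does not exist for a subject reprimed before Day 57.

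**The case against.** The strongest reply is that the conflict will seldom bite. From Day 15 to Day 57 dosing is weekly, so a gap of 15 to 27 days means two or three missed weekly doses in a row. Section 6.6.2 says magrolimab should in general not be delayed, and Section 6.7 says a missed dose should be given as soon as possible. Sections 6.6.2 and 6.6.2.1 also require that the Medical Monitor be told of planned delays, which gives a central point where handling could be made uniform. This stands as a limit on size. It does not settle the rule: notification is not a decision rule, and nothing states which section prevails.

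One may also read the opening of Section 6.6.2.1 as a general statement that its two items refine. That would remove the conflict within the section, apart from the 28-day boundary. The conflict with Section 4.5 remains, because an exception confined to subjects without a 30 mg/kg dose implies that other subjects have the longer allowance.

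A reader might infer more than the documents support:
- *That the post-repriming texts contradict each other.* They do not. Starting after 7 days is permissive and fits a return to 14-day dosing from repriming Day 29. What remains is an ambiguity for a subject who never began maintenance.
- *That repriming is stated to exist to limit anemia.* Section 4.6.2 gives that reason for the initial priming dose; Section 6.6.2.1 gives the antigen sink. Anemia is relevant only through the hemoglobin checks.
- *That sites will in fact treat differently.* The documents show that they can.
- *That a co-primary test is affected.* Adverse events, DLTs and CR rate are listed as primary endpoints, but no co-primary testing is defined. Anemia is not a listed DLT (Section 8.5.6), so the clearest effect is on adverse events.

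**Conclusion.** The contradiction is real and is an internal inconsistency in the dosing text. Its main part is the trigger: opposite instructions at gaps of 15 to 27 days after any of the seven 30 mg/kg priming doses. The infusion-time conflict for repriming also holds. The collision at exactly 28 days from Day 57 is real but minor, and the undefined clock (delay or interval) makes the boundaries less certain still. The rules agree for gaps of 14 days or less and for gaps above 28 days. A and B also agree before the first 30 mg/kg dose.

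These statements rest on the literal reading and assumptions set out in the working. The number of subjects affected cannot be estimated, because the protocol gives no frequency for such gaps. No sample-size or error-rate figure changes. The point should be corrected because it bears on safety and is cheap to settle.

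**What to change.** Reconcile Sections 1.1, 4.5 and 6.6.2.1 and Tables 2, 4 and 6 so that the same text appears in each:
- one repriming trigger per treatment period, including whether the bracket on doses below 30 mg/kg applies;
- one definition of the gap (days since the last dose, or days past the due date) and one handling of exactly 28 days;
- one infusion duration for the repriming doses.

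Also state what follows repriming for a subject who had not started maintenance. Which rule is adopted is a clinical choice for the sponsor. The cost is protocol wording and a notice to sites; no change to the sample size or the statistical analyses is needed.
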